### **Secondary Endpoints**

There are 4 secondary endpoints of interest in this study. No adjustments for multiple comparisons/testing will be performed for the other secondary endpoints. Analyses will be based on the observed data using the FAS.

The secondary endpoints are:

- Hb increment
  - Calculation:  $[(\text{post-transfusion Hb} - \text{pre-transfusion Hb})/\text{Hb transfused}]/\text{RBC volume in subject at pre-transfusion}$
  - Hb transfused in the above formula is the sum of Hb content of each unit transfused calculated as  $(\text{Hb/dL} \times \text{volume})/100$
  - Note: RBC volume in subjects at pre-transfusion is based on weight, height, sex, and pre-transfusion Hct. Example formulas are provided below where weight is in pounds and height is in inches.
  - RBC Volume (Male) =  $[(0.006012 \times \text{height}^3)/(14.6 \times \text{weight}) + 604] \times (\text{Hct}/100)$
  - RBC Volume (Female) =  $[(0.005835 \times \text{height}^3)/(15 \times \text{weight}) + 183] \times (\text{Hct}/100)$
- Actual Hb level post-transfusion (15 min)
- Proportional decline in post-transfusion Hb level
  - Calculation:  $[(\text{Hb (t0)} - \text{Hb(t1)})/\text{Hb(t0)}]/\text{time between transfusion (days)}$
- RBC mass infused (volume x Hb/unit)

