Abbreviations: AE = adverse event, BP = blood pressure, CBC = complete blood count, HR = heart rate, ICF = informed consent form, K = potassium, Na = sodium, RBC = red blood cell, RR = respiratory rate, SAE = serious adverse event, SpO₂ = arterial oxygen saturation via pulse oximetry, UADE = unanticipated adverse device effect.

^a The ICF/parental consent/assent process may take place prior to the 28-day screening window.

^b Medical/surgical history should include thalassemia diagnosis information (ie, genotype [if available], phenotype, history of antibody formation [list of antibodies] and date of diagnosis); transfusion history (date of transfusion initiation, history of transfusion reactions in the previous 6 months [type, date], mean transfusion interval for the prior 6 months); and splenectomy status, immunizations, infection exposures in the 3 months prior to the screening visit, current organ dysfunction.

^c Height will be measured once at the screening visit. Weight will be measured prior to each transfusion.

^d If screening procedures confirm eligibility, the subject will be randomized within 10 days prior to initiation of the first study transfusion (Study Day 0).

^e Document RBC product details for each unit transfused per Section 13.3.

^f As per the AABB Technical Manual, the initial flow rate for RBC transfusions should be 1-2 mL/min (60-120 mL/hr) for the first 15 minutes, with the total infusion duration ≤ 4 hours.⁴¹

^g A full physical exam will be conducted at the screening visit and will include examination of general appearance, skin, eyes/ears/nose/throat, head/neck, pulmonary, chest, cardiovascular, abdominal and liver/spleen, lymphatic, musculoskeletal, and neurological. Abbreviated physical exams will be conducted prior to the first transfusion of Treatment Period 2 and at the Final Follow-up Visit, and will include examination of general appearance, eyes/ears/nose/throat, pulmonary/chest, cardiovascular, abdominal, and neurological.

^h Vital sign measurements will include HR, BP, RR, SpO₂, and temperature. On the days of transfusion, vital sign measurements will be obtained within 1 hour prior to transfusion, during transfusion at 15 (± 5) minutes and hourly, at end of transfusion, and 15 (± 5) minutes after end of transfusion. All vital sign measurements should be collected within ± 15 minutes of the nominal time point unless otherwise specified.

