22.4 Sponsor Responsibilities

22.4.1 Amendments to the Clinical Investigation Plan

Any amendment to the CIP, as deemed appropriate by the Sponsor, will be implemented as the study progresses. Amendments will be submitted to the IRB/EC for written approval before implementation.

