### **B. Protocol and Amendment History**

This Statistical Analysis Plan (SAP) is based on version 4.1 /28AUG2017 of Protocol CTS-5056, which will incorporate Amendment x.

This SAP will govern the analysis of data from this study. Any modifications to the SAP will be done by a blinded statistician without access to the study data prior to database lock. Any deviations from the SAP, including any after database lock, will be documented as such in the clinical study report.

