## **C. Secondary Efficacy Endpoints Analyses**

Hb increment, proportional decline in post-transfusion Hb and RBC mass infused will each be analyzed separately with a mixed effects repeated measures model fitting fixed effect terms for treatment, period and treatment\*period interaction. Subject will be included in the model as a random effect. The point estimates and associated 95% confidence intervals will be presented for the treatment differences.

Two analyses will be carried out for the 15 minute Hb value.

- The first is directed at estimating the difference between the MIR RBC and REF RBC products and for this the mixed-effect model used for the primary outcome will be adopted to model the 15 minute Hb value as the response. A 95% confidence interval for the estimated mean difference in the 15 minute Hb value will be computed.
- A second analysis will report the proportion of 15 minute Hb values within the pre-specified range of plus or minus 15% of the target value. This target value is specified at the start of study and should remain fixed during the course of the study. This success rate will be estimated using generalized estimating equations with this binary response, a logistic link, a main effect for product type (MIR vs. REF RBCs) and an exchangeable correlation matrix to accommodate the dependence within patients. The resulting estimates will be provided as supplementary information to help in the

interpretation of the primary analyses. There will be no non-inferiority bound or formal tests associated with these event rates.

All secondary endpoints will be descriptively summarized by treatment. Additionally, Hb increment, proportional decline in post-transfusion Hb and RBC mass infused will be presented graphically.

As a secondary analysis, actual Hb AUC will also be analyzed similarly to the primary endpoint described in Section VIII.B. Specifically, the Hb AUC will not be normalized to the 15-minute post-transfusion Hb level in this analysis.

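### The printed RBC volume formulas for Hb increment divide height cubed by weight, so the result hardly depends on body size and differs about 3.3-fold between the sexes

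*SAP*

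**What the plan says.** Hb increment is the first of four secondary efficacy endpoints. SAP Section VIII.A (Secondary Endpoints) and protocol Section 21.7.1.2 define it as the Hb rise divided by the Hb transfused, divided again by the subject's red-cell volume before transfusion. On that volume the SAP says: "Note: RBC volume in subjects at pre-transfusion is based on weight, height, sex, and pre-transfusion Hct". It continues: "Example formulas are provided below where weight is in pounds and height is in inches".

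Both documents then print the same two formulas:

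- Men: [(0.006012 × height³) / (14.6 × weight) + 604] × Hct/100
- Women: [(0.005835 × height³) / (15 × weight) + 183] × Hct/100

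No output unit is given, and neither document offers another formula. Footnote c to protocol Table 14-1 says: "Weight will be measured prior to each transfusion". Under SAP Section VIII.C, Hb increment and two other secondary endpoints "will each be analyzed separately with a mixed effects repeated measures model", with treatment, period and their interaction as fixed effects and subject as a random effect. No transformation and no sex term are mentioned.

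**The concern.** A blood or red-cell volume based on height and weight should rise with both. The printed formulas put weight in a denominator, so computed volume falls as weight rises. The height-cubed term is also divided by a number of similar size. The quotient is then tiny next to the added constant, and the bracket is little more than a sex code.

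The volume is the final divisor of the endpoint, so an error in it passes straight into every Hb increment value. As printed, the divisor supplies almost no size adjustment and puts men and women on very different scales. A random subject intercept absorbs differences in level between subjects. It does not absorb a subject-specific scaling of the treatment difference itself.

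**Working it through.** The plan gives no worked red-cell volume, so there is no figure to reproduce. The check evaluates the printed formulas. Body sizes, hematocrit and sex split are assumptions; the documents give none of them.

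**1. Two worked subjects**

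- Man, 68 in, 154 lb: 0.006012 × 314,432 = 1,890.4; 14.6 × 154 = 2,248.4; quotient 0.84; bracket 604.84.
- Woman, 64 in, 120 lb: 0.005835 × 262,144 = 1,529.6; 15 × 120 = 1,800; quotient 0.85; bracket 183.85.

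**2. Range of the bracket**

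| Heights and weights | Quotient, men | Bracket, men | Quotient, women | Bracket, women |
|---|---|---|---|---|
| 60–72 in, 90–220 lb | 0.40–1.71 | 604.4–605.7 | 0.38–1.61 | 183.4–184.6 |
| 52–76 in, 60–300 lb | 0.19–3.01 | 604.2–607.0 | 0.18–2.85 | 183.2–185.9 |

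The wider grid allows for entry from age 12 (protocol Section 11.2) and includes implausible combinations. Even there the bracket barely moves.

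**3. Direction of the weight effect**

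- A 10% weight gain changes the bracket by −0.01% for the man above and −0.04% for the woman.
- From 90 to 220 lb, a 66-inch man goes from 605.32 to 604.54 (−0.13%), and a 64-inch woman from 184.13 to 183.46 (−0.36%).

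**4. Ratio between the sexes**

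At the same size (68 in, 154 lb) and the same hematocrit, 604.84 / 183.79 = 3.29. Over the narrower grid the ratio is 3.27–3.30.

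**5. Plausibility against the protocol's own data**

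Protocol Table 19-5, Mirasol units at 21 days: 50.69 g total Hb / 19.16 g/dL = 264.6 mL; × 56.66% Hct = about 150 mL of red cells in one unit. Reading the formula's output as mL at Hct 27–33%:

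- the woman's whole-body red-cell volume is 183.85 × 0.27 to 0.33 = 50–61 mL;
- the man's is 604.84 × 0.27 to 0.33 = 163–200 mL.

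A single unit would hold about 2.5 to 3 times the woman's entire red-cell volume.

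**6. Illustration of the effect on the model**

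Assume no transformation, and equal hematocrit, equal Hb rise per gram transfused and equal coefficient of variation in both sexes. Let r = 3.29 be the scale of women relative to men and p the share of women.

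- Women's share of the pooled difference = pr / (pr + 1 − p)
- Efficiency relative to equal scale = (pr + 1 − p)² / (pr² + 1 − p)
- Relative width of the confidence interval = 1 / √efficiency

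| p | Women's share | Efficiency | Relative CI width |
|---|---|---|---|
| 0.4 | 0.687 | 0.745 | 1.159 |
| 0.5 | 0.767 | 0.778 | 1.134 |
| 0.6 | 0.832 | 0.817 | 1.106 |

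**The case against.** The strongest reply concerns impact rather than arithmetic.

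- **The formulas are only examples.** The note is the rule, and a programmer could apply a better formula. But neither document supplies one, and SAP Section I.B says "This SAP will govern the analysis of data from this study". The programmer must either code what is printed or choose something not pre-specified.
- **The 77% and 13% figures are illustrative.** This stands. They assume an equal Hb rise per gram in both sexes, while the transfusion-volume formula in protocol Section 14.3 implies a smaller rise per mL in heavier subjects. Allowing for that moves women's share up, to about 82% at an even split under assumed average sizes. The tabulated ranges vary only the sex split, so they understate the uncertainty.
- **Equal scale is not what a correction delivers.** This also stands. Rise per gram already falls with body size, so dividing by a volume that grows with size steepens that dependence within each sex. Correction removes the artificial 3.3-fold sex factor. It does not make the increment independent of body size.
- **The endpoint is minor.** It has no non-inferiority bound and no multiplicity control, and each subject's ratio of Mirasol to reference values is largely kept. If the proportional effect is the same in both sexes, no sex-related bias follows. This limits the severity but does not remove the error.
- **The slash might be a PDF-reading fault.** This is unlikely. It appears in all four printings with explicit parentheses, and the plus sign in the same lines was read correctly. The originals would settle it.

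**Conclusion.** The concern holds. As printed, the formulas return in effect a sex constant (about 605 or 184) times hematocrit, contrary to the note above them. The values are implausible when read as mL. This conclusion needs only an ordinary range of heights and weights.

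At equal hematocrit, Hb increment is on a scale about 3.3 times larger in women than in men. If it is modelled untransformed, the pooled difference is dominated by women (about 77% at an even split, 69–83% at 40–60% women). The interval is about 13% wider relative to the effect than with equal scale (11–16%). Those figures rest on the assumptions in the illustration and should be read as indicative.

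The damage is confined to this secondary endpoint. The primary endpoint, the 20% margin and the sample size do not use the formula. It should be corrected, but it does not threaten the trial's main conclusion.

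**What to change.** Before database lock:

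1. Check both formulas against the sponsor's source.
2. Correct SAP Section VIII.A and protocol Section 21.7.1.2 so that computed volume rises with height and with weight, as the note says. A sum of the height term, the weight term and the constant is the likely intended form. That is an inference for the sponsor to confirm, since neither document prints it.
3. Present one definitive formula per sex instead of an example, state the output unit, and add a worked value so that programming can be verified.

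The cost is small. Height, weight, sex and hematocrit are already collected, so no new data are needed. The SAP needs a correction before lock. The matching protocol correction may need ethics approval, because protocol Section 22.4.1 says: "Amendments will be submitted to the IRB/EC for written approval before implementation".

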The results from this study indicated that RBCs derived from Mirasol-treated WB maintained an acceptable cell quality and recovery as compared to untreated RBCs in accordance with FDA criteria. The geometric least squares (LS) mean of the AUC of RBC survival following Mirasol treatment was approximately 83% of that for untreated control. The mean linear RBC survival

was shorter following Mirasol treatment (60.49 days) compared with the mean RBC survival of untreated control (81.57 days). Subjects reinfused with Mirasol-treated LR-RBCs demonstrated no evidence of neoantigenicity or other major safety concerns. In light of previous nonclinical data supporting the efficacy of Mirasol treatment in reducing pathogens and residual WBCs, this study further supported the use of Mirasol treatment of WB as a means to increase the safety of RBC transfusions.

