11.2 Inclusion Criteria

Subjects will be eligible for inclusion only if all of the following criteria apply:

1. Transfusion dependent thalassemia patient with mean 2-4 week transfusion intervals for the prior 6 months.
2. Age \geq 12 years.
3. Negative pregnancy test for women of childbearing potential and agreement to practice a medically acceptable contraception regimen throughout the participation in the clinical trial. Not required if female subjects are not of child-bearing potential (ie, prior to menses onset, surgically sterilized, 1-year postmenopausal).
4. Signed informed consent from the patient, or if the patient is $<$ 18 years of age, signed assent from patient and consent from parent/guardian, according to local Institutional Review Board/Ethics Committee (IRB/EC) requirements.

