19.3.3 Risk of Increased Transfusion Frequency

The recovery and survival in vivo studies have demonstrated that compared to conventional untreated RBCs, RBCs derived from Mirasol-treated WB have reduced recovery, although still within acceptable therapeutic ranges. Specifically, the mean recovery of Mirasol-treated RBCs was 82.5% compared with 91.7% for untreated RBCs. The RBC area under the curve (RBC AUC), a measure of RBC survival, was 16.7% lower in transfused Mirasol-treated RBCs. Because of these differences, patients receiving RBCs derived from Mirasol-treated WB may require more frequent RBC transfusions and/or more units of RBCs per transfusion as compared to conventional RBCs. Transfusion frequency will be evaluated in this study to determine if there

is an increase for subjects receiving RBCs derived from Mirasol-treated WB when compared to conventional RBCs.

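### Hb increment is divided by a red-cell volume that contains pre-transfusion Hct, which biases it towards the product leaving the lower Hct and can mask or reverse a real deficit

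*SAP*

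**What the plan says.** Hb increment heads the list of four secondary efficacy endpoints. Protocol 21.7.1.2 and SAP VIII.A (Secondary Endpoints) define it identically: post- minus pre-transfusion Hb, divided by grams of Hb transfused, and that quotient divided again by "RBC volume in subject at pre-transfusion". Both add that "RBC volume in subjects at pre-transfusion is based on weight, height, sex, and pre-transfusion Hct" and print example formulas, with height in inches and weight in pounds:

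- Male: [(0.006012 × height³)/(14.6 × weight) + 604] × (Hct/100)
- Female: [(0.005835 × height³)/(15 × weight) + 183] × (Hct/100)

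SAP VIII.C analyses the endpoint in a mixed model with "fixed effect terms for treatment, period and treatment\*period interaction" and a random subject effect, and reports the treatment difference with a 95% confidence interval. SAP VI.D adds pre-transfusion Hb as a covariate, but only in the primary analysis. No non-inferiority margin is attached to Hb increment. Neither document says which post-transfusion Hb enters the formula, or that a higher value is better.

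**The concern.** There are two problems with the divisor.

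First, it contains something the treatment can move. Within a subject in a crossover, sex and height are fixed and weight changes little, so Hct is the only part of the divisor likely to differ between products. The assessed transfusions follow a 50-day wash-in on the assigned product. Protocol 14.3 calculates the volume from a target post-transfusion Hb fixed at baseline. If the interval does not change, poorer cell survival then shows up as a lower Hct before the next transfusion. A lower Hct shrinks the divisor and raises the index, and the model has no term to take this out.

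Second, the size correction is inverted. Hb rise per gram transfused is already roughly proportional to 1/blood volume, so correcting for body size means multiplying by blood volume, not dividing.

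What is at stake is the one secondary endpoint that directly measures rise per gram given. Protocol 19.3.3 warns of a deficit of this kind, and the primary endpoint, being normalised to the 15-minute Hb, does not measure it.

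**Working it through.** The documents state no expected value for Hb increment, so there is no plan figure to reproduce. The check evaluates the printed formula.

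**Inputs.** Recovery, Protocol 19.3.3: "Specifically, the mean recovery of Mirasol-treated RBCs was 82.5% compared with 91.7% for untreated RBCs", a ratio of 82.5/91.7 = 0.900. Mean linear survival, Protocol 5.2: 60.49 days for Mirasol and 81.57 days for untreated cells. Interval, Protocol 11.2: "mean 2-4 week transfusion intervals for the prior 6 months". The documents do not give the Hct difference between products, so it is an assumption shown as a range, starting from an illustrative Hct of 29.

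**1. Effect of Hct within a subject.** With the height, weight and sex terms common to both periods,

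index ratio MIR/REF = (ratio of rise per gram) × (REF pre-Hct / MIR pre-Hct).

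| MIR pre-Hct (REF = 29) | Equal rise per gram | Rise follows 0.900 |
|---|---|---|
| 29 (level) | 1.00 | 0.90 |
| 27.55 (5% lower) | 1/0.95 = 1.053 | 0.95 |
| 26.1 (10% lower) | 1/0.90 = 1.111 | 1.00 |
| 24.16 (16.7% lower) | 1/0.833 = 1.200 | 1.08 |

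Break-even is where the Hct ratio equals the rise ratio: a 10.0% relative fall, if the full recovery ratio carries over to the rise.

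**2. How large the Hct gap could be.** This is an illustrative steady-state model with linear survival L, the same interval T in both periods and the same post-transfusion Hb. The fraction surviving after k intervals is s_k = max(0, 1 − kT/L). With S = Σ s_k, pre/post = (S − 1)/S. If a share e of post-transfusion Hb is constant and endogenous, pre/post = e + (1 − e)(S − 1)/S. For T = 14 and e = 0, untreated S = 3.425 gives 0.708 and Mirasol S = 2.686 gives 0.628, a ratio of 0.886.

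| T (days) | e | Pre-Hct ratio MIR/REF | Index ratio, equal rise | Index ratio, rise × 0.900 |
|---|---|---|---|---|
| 14 | 0 | 0.886 | 1.128 | 1.015 |
| 14 | 0.5 | 0.953 | 1.049 | 0.944 |
| 21 | 0 | 0.826 | 1.211 | 1.090 |
| 21 | 0.5 | 0.935 | 1.069 | 0.962 |
| 28 | 0 | 0.770 | 1.298 | 1.168 |
| 28 | 0.5 | 0.924 | 1.082 | 0.973 |

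In this model a true ratio of 0.90 would be reported as anything from 0.94 to 1.17: always understated, sometimes reversed.

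**3. The printed bracket.** At 66 in, height³ = 287,496. At 150 lb:

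- Male: 1,728.4/2,190 + 604 = 604.8
- Female: 1,677.5/2,250 + 183 = 183.7

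The height and weight term contributes less than 1. At Hct 29, going from 100 to 200 lb moves the printed red-cell volume only from 175.5 to 175.3 (male) and from 53.4 to 53.2 (female), a change of 0.3% or less. These are not plausible blood or red-cell volumes in mL. Within a sex, the printed divisor is in effect a constant times Hct.

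**4. Body size.** Take two same-sex subjects with the same recovery and Hct but blood volumes of 3.0 and 5.5 L (illustrative). Rise per gram differs by 5.5/3.0 = 1.83-fold, and the near-constant printed bracket leaves that difference uncorrected.

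**The case against.** The strongest case against is that the treatment bias needs a difference in pre-transfusion Hct that no document predicts. Treating physicians set volume and frequency, and Protocol 19.3.3 itself expects that Mirasol recipients may need more frequent transfusions or more units. If practice keeps pre-transfusion Hct level, the bias between products is zero. Linear survival of 60 to 80 days also means that a 50-day wash-in leaves some of the previous product's cells in circulation, so Hct is not purely an effect of the assigned product. Both points stand, and both make the bias conditional.

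The 0.90 ratio is also borrowed. It comes from autologous 21-day-old cells in healthy volunteers, in a study whose primary criterion was 24-hour recovery. The documents do not say how much of that loss shows in the Hb rise used here. Reference units in this trial may be stored for up to 42 days, washed or irradiated. This stands too: 0.90 is a worked example, not the trial contrast.

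Finally, other planned measures lack this divisor: 15-minute Hb, proportional decline, RBC mass infused and un-normalised Hb AUC. A deficit could show there. That limits the harm but does not make the index right, since none of those is a rise per gram.

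Two stronger readings are tempting. A reader might infer that the product with poorer survival always scores higher. The documents do not support that, because poorer recovery also lowers the numerator; with it included, the model gives ratios on both sides of 1. A reader might also infer a (5.5/3.0)² = 3.4-fold distortion by body size. That holds only if the bracket returns a true blood volume, and as printed it does not.

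**Conclusion.** The definition should be corrected. Hb increment is inversely proportional to pre-transfusion Hct, which the assigned product can lower, and its model has no term for it. The index is therefore biased towards the product with the lower pre-transfusion Hct: by 5.3% at a 5% lower Hct and 11.1% at a 10% lower Hct, for equal rise per gram. It can hide or reverse a true deficit. Reversal requires the relative fall in Hct to exceed the relative loss in rise per gram, about 10% if the IMPROVE II recovery ratio applies. The reversed size scaling and the implausible bracket do not depend on any assumption about Hct.

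The consequence is limited to one secondary endpoint, reported as an estimate with an interval and no margin. Nothing here touches the primary endpoint or its non-inferiority test.

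**What to change.** In Protocol 21.7.1.2 and SAP VIII.A, in this order:

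1. Correct the height, weight and sex bracket so that it returns a plausible blood volume, and confirm it against the sponsor's source. For example, with the terms added instead of divided, the printed male coefficients give 1,728 + 2,190 + 604, about 4,520 mL, at 66 in and 150 lb.
2. Define Hb increment as [(post Hb − pre Hb) in g/dL × estimated blood volume in dL] / Hb transfused in g, with no Hct factor. The units cancel, and the result reads as the fraction of transfused Hb recovered, with higher meaning better.

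The order matters: multiplying by the bracket as printed (about 6.0 dL for men and 1.8 dL for women) would not give a recovery fraction.

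At a given rise per gram, the product comparison then no longer depends on Hct: 1.00 at equal rise, and 0.90 if the rise follows reported recovery. Some dependence can remain in the rise itself. In a dilution model with assumed values (7 dL at 19.2 g/dL added to 40 dL, all of it still circulating), rise per gram is 0.01053 from a starting Hb of 9.7 g/dL and 0.01108 from 9.2 g/dL, about 5% more. The fix removes the extra distortion from the divisor, not this.

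The cost is one definition in two documents, plus programming. No new data are needed. Values will not be comparable with any earlier use of the printed formula.
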